6.2.5. Other Exploratory Continuous Endpoints (Repeated Visits)

For Part 1, continuous exploratory endpoints will be descriptively summarized by treatment group and by visits for percentage change from baseline in EASI score and change from baseline in POEM.

For Part 1 OLE, continuous exploratory endpoints at all visits from Week 20 up to Week 68 (eg, percent change from baseline in EASI score), will be analyzed using a single MMRM without imputation for missing data (Section 5.2.2.2). The model will include all data from Part 1 DB Week 4 up to Part 1 OLE Week 68 on the FAS (Appendix 3). The actual stratification factor (ie, baseline IGA of 3 or 4) from clinical database will be used in the MMRM analysis. This analysis will provide the LSM of the treatment groups by visit, the LSM of the treatment difference by visit (Etrasimod 2 mg QD versus Placebo → Etrasimod 2 mg QD from Week 20 to Week 68; results from Week 4 to Week 16 will not be displayed from this analysis since they will come from a repeated analysis of the Part 1 DB phase for this endpoint) in percent change from baseline in EASI score, 95% CI and the 2-sided p-value by visit (Section 5.2.2.2). This approach is also similary applied to change from baseline in

POEM including all data at Part 1 DB Week 16 (Etrasimod 2 mg QD versus Placebo), Part 1 OLE Weeks 32 and 68 (Etrasimod 2 mg QD versus Placebo → Etrasimod 2 mg QD) on the FAS. Results from all visits will be displayed.

For Part 2 OL Safety phase, continuous exploratory endpoints at all visits will only be descriptively summarized for the single treatment group of Etrasimod 2 mg QD using only observed values on the FAS (since intercurrent events are not considered in this Part 2 OL Safety phase). Therefore, missing values will not be imputed in this Part 2 OL Safety phase. This approach is applicable to percent change from baseline in EASI score and change from baseline in POEM score, at all visits from Week 4 to Week 52. The baseline is the pre-dose Day 1 of Part 2 OL Safety phase (Section 3.4).

6.3. Subset (Subgroup) Analyses

For Part 1 DB, subgroup analyses are only performed for the primary endpoint of IGA response at Week 16 under the primary estimand (ie, Estimand E1) including only the preintercurrent-event data on the FAS analyzed for participants with baseline IGA \geq 2. The treatment comparison of Etrasimod 2 mg QD vs. Placebo for the primary endpoint at Week 16 will be assessed at each level of the subgroup variables.

The following subgroup variables will be considered:

- Baseline IGA score 2 levels (3, 4), based on actual clinical data.
- Sex 2 levels (Female, Male).
- Age at baseline -2 levels (18 <50 years, \ge 50 years).
- Race 2 levels (White, Non-White).
- BMI at baseline 2 levels ($<30, \ge 30 \text{ kg/m}^2$).
- AD disease duration since diagnosis by Hanifin and Rajka criteria (Hanifin and Rajka, 1980) − 2 levels (<5, ≥5 years).
- Prior systemic corticosteroid failure only 2 levels (Yes, No).

Estimates of the treatment difference between etrasimod 2 mg QD and placebo for the primary endpoint (primary estimand) along with the 95% CI without p-value, will be presented for each level of a subgroup variable. The normal approximation using CMH approach adjusting for actual stratification factor of IGA score (Section 3.4.1) will be used for each level of a subgroup variable, except for the subgroup of baseline IGA score.

For the subgroup of baseline IGA score (2 levels of 3 or 4), the normal approximation approach to the difference in binomial proportions on the FAS will be used. For each level of baseline IGA score (3 or 4), the 95% CI of the treatment difference is calculated as:

$$(\hat{p}_A - \hat{p}_B) \pm z_{0.975} \sqrt{\frac{\hat{p}_A (1 - \hat{p}_A)}{n_A} + \frac{\hat{p}_B (1 - \hat{p}_B)}{n_B}}$$

where \hat{p}_A and \hat{p}_B represent the estimated response rates for etrasimod 2 mg QD and placebo respectively, and n_A and n_B are their respective sample sizes. $z_{0.975}$ is the 97.5th percentile of the standard normal distribution. No p-value will be produced for subgroup analyses. The method of handling 0 or 100% response rate in either or both treatment groups can be found in Section 5.2.1.1.

The primary purpose of subgroup analyses is to check for consistency of the primary endpoint results across subgroup levels, ie, making sure overall results are not driven by some subset of participants (ie, particular level of a subgroup variable). Graphical display (eg, forest plot) of the treatment differences in IGA response at Week 16 (primary estimand) between etrasimod 2 mg QD and placebo by subgroups will be presented. There is no intention to have any specific inference within subgroup variables, therefore only 95% CI's are produced without corresponding p-values.

6.4. Baseline and Other Summaries and Analyses

6.4.1. Baseline Summaries

For Part 1 and Part 2 of this study, similar demographics and baseline characteristics will be included but may not be limited to the ones listed below. These characteristics will be summarized descriptively. For continuous variables, the summary will include N (which is the number of participants evaluable for the baseline characteristics), mean, median, SD and range (ie, minimum and maximum). For binary and categorical variables, the summary will include frequencies and percentages. A missing category will be included for those participants with missing value. Some ordinal variables may also be summarized as continuous variables. In addition to displays by treatment group, the summaries will also be provided for all the treatment groups combined.

Demographic characteristics:

- Baseline age (continuous in years);
- Baseline age categories (≥ 16 to < 18, ≥ 18 to < 50, ≥ 50 to < 70, ≥ 70 years);
- Gender (Female, Male);
- Race (categories as reported in Demographics CRF);

- Ethnicity (Hispanic/Latino or Spanish origin, Not Hispanic/Latino or Spanish original, Not Reported);
- Baseline body weight (continuous in kg);
- Baseline body weight categories ($<60, \ge 60 \text{ to } \le 100, >100 \text{ kg}$);
- Baseline height (continuous in cm);
- Baseline BMI (continuous kg/m²);
- Baseline BMI categories (<18.5, ≥18.5 to <25, ≥25 to <30, ≥30 to <40, and ≥40 kg/m²).

Baseline disease characteristics:

- AD disease duration since diagnosis by Hanifin and Rajka criteria (continuous in years);
- AD disease duration since diagnosis categories by Hanifan and Rajka criteria (<5, ≥5 years);
- Baseline IGA (3, 4) Actual in Database (note that baseline IGA of values ≤2 will also be summarized if recorded, as they are protocol deviations);
- Baseline IGA (3, 4) Reported in Randomization;
- Baseline EASI score (continuous);
- Baseline Total BSA (continuous in %);
- Baseline PP-NRS (continuous);
- Baseline PP-NRS categories ($<4, \ge 4$);
- Baseline Skin Pain NRS (continuous);
- Baseline Skin Pain NRS categories (<4, ≥4);
- Baseline POEM (continuous);
- Baseline POEM categories ($<4, \ge 4$);
- Prior Systemic Therapies (Biologics, JAK inhibitors, conventional systemic therapies).

6.4.2. Study Conduct and Participant Disposition

Study conduct and participant disposition is summarized by frequency and percentages for the following sets by treatment group for Part 1 and Part 2.

- Total number of participants screened;
- Number of participants who failed screening;
- Number of participants randomized;
- Number of participants randomized and treated;
- Number of participants in the FAS;
- Number of participants in the FAS who discontinued from the study due to any reason (for Part 1 DB phase, this will be DB phase);
- Number of participants in the FAS who completed the study (for Part 1 DB phase, this will be DB phase);
- Number of participants in the SAS.

Participants who are treated but are not randomized will also be summarized if at least one participant falls into this category.

6.4.3. Study Treatment Duration

Within any study phases (Part 1 DB, Part 1 DB+OLE, or Part 2 OL Safety), study treatment duration (in day) is defined as the time from the day of first dose (ie, Day 1) to the day of last dose of the study treatment. Besides descriptive summaries of the study treatment duration, the number of participants (%) will also be summarized by the following categories (where the upper limits correspond to the target day of the visit windows, Appendix 2.1), and ≥ categories, which are aligned with the protocol's study visits.

 Table 5.
 Reporting Categories for Study Treatment Duration (in Day)

Part 1 DB		Part 1 DB + OLE		Part 2 OL Safety	
Categories	≥ Categories	Categories	≥ Categories	Categories	≥ Categories
(day)	(day)	(day)	(day)	(day)	(day)
1	≥ 1	1	≥ 1	1	≥ 1
2 - 29	≥ 2	2 – 29	≥ 2	2 - 29	≥ 2
30 - 57	≥ 30	30 - 57	≥ 30	30 - 57	≥ 30
58 – 85	≥ 58	58 - 85	≥ 58	58 – 113	≥ 58
86 - 113	≥ 86	86 – 113	≥ 86	114 – 169	≥ 114
≥ 114	≥ 114	114 – 141	≥ 114	170 - 253	≥ 170
		142 – 169	≥ 142	254 - 309	≥ 254
		170 - 225	≥ 170	310 – 365	≥ 310
		226 – 281	≥ 226	≥ 366	≥ 366
		282 - 365	≥ 282		

DMB02-GSOP-RF02 7.0 Statistical Analysis Plan Template 31-Jan-2022

Part	Part 1 DB		Part 1 DB + OLE		Part 2 OL Safety	
Categories	≥ Categories	Categories	≥ Categories	Categories	≥ Categories	
(day)	(day)	(day)	(day)	(day)	(day)	
		366 – 477 > 478	≥ 366 > 478			

Table 5. Reporting Categories for Study Treatment Duration (in Day)

The upper limit of period category corresponds to visit window's target day (target week x 7 days + 1 day).

6.4.4. Prior and Concomitant Medications and Nondrug Treatments

Prior medications and non-drug treatments which start prior to baseline (ie, Day 1) will be summarized by treatment group and study phases. Concomitant medications and non-drug treatments which were taken any time during the study treatment period will also be summarized by treatment group and study phases. In addition, Concomitant (Day 1) medication and non-drug treatments may also be summarized for those medications and non-drug treatments taken at baseline (ie, Day 1). All summaries will be coded to the WHODrug version at the time of database release and this version will be noted in the summaries.

6.5. Safety Summaries and Analyses

All the safety data will be summarized descriptively through appropriate data tabulations, descriptive statistics, and graphical presentations. Treatment-emergent AEs including SAEs and AE leading to discontinuation of study treatment, vital signs, 12-lead ECG parameters, and laboratory tests, etc. will be summarized according to the Clinical Data Interchange Standards Consortium (CDISC) and Pfizer Standards (CaPS). All safety analyses will be performed on the SAS (Section 4.2).

6.5.1. Adverse Events

The MedDRA version for AE coding at the time of database release will be adopted and the version used will be displayed in all relevant safety data tabulations. TEAEs will be displayed by these 3 phases: (1) Part 1 DB (up to Week 16), (2) Part 1 DB+OLE (up to Week 68), (3) Part 2 (up to Week 52), using the same treatment group labels (Section 5.2). Safety data from follow-up visits will also be be included for summaries.

In general, all treatment-emergent AE are tabulated in standard safety displays. AESIs will be summarized descriptively only (Section 3.5.2). The number and percent of participants reporting specific past and present medical histories at screening or baseline will be summarized by medical history reporting term (MedDRA) and treatment group following CaPS.

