7.1.5. Lack of Efficacy

Lack of efficacy will result in permanent discontinuation of study intervention only for the reason below:

 Participants who do not meet EASI-50 criteria at Week 32 in Part 1 (Week 16 of OLE) or at Week 16 of Part 2. In the case of lack of efficacy, the participant will be permanently withdrawn from administration of study intervention, complete Early Termination procedures, and then complete the 2- week (SFU 1) and 4-week (SFU 2) follow-up visits.

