2.2. Study Objectives, Endpoints, and Estimand

Table 3. Objectives, Endpoints, and Estimands

Type	Objective	Endpoint	Estimand
Primary			
Efficacy	Part 1 DB: To evaluate the efficacy of etrasimod 2 mg QD versus placebo in adult participants with moderate-to-severe AD and a history of a prior systemic therapy failure.	• Proportion of participants achieving IGA of clear (0) or almost clear (1) (on a 5-point scale) and a reduction of ≥2 points from baseline at Week 16.	• Estimand E1 (Primary Estimand): The difference in the proportions of the binary endpoint between etrasimod 2 mg QD and placebo in patients with moderate-to-severe AD and a history of a prior systemic therapy failure. More details of Estimand E1 (Primary Estimand) are described in Section 2.2.1.
Safety (depending on Part 1 DB IA results)	Part 1 OLE and Part 2 OL Safety: To evaluate the long-term safety of oral etrasimod 2 mg QD in adult participants with moderate-to-severe AD and a history of a prior systemic therapy failure.	 Incidence and severity of treatment-emergent AEs, AEs leading to study treatment discontinuation, SAEs, and AESIs. Incidence of clinically significant changes in clinical laboratory values, 	Not applicable.

Table 3. Objectives, Endpoints, and Estimands

Type	Objective	Endpoint	Estimand
		ECG measurements and vital signs.	
		Note: Baseline for Part 1 is the pre-dose Day 1 in Part 1. Baseline for Part 2 is the pre- dose Day 1 in the Part 2 OL Safety phase.	
Secondary	D +1DD 77		
Efficacy	Part 1 DB: To evaluate the efficacy of etrasimod 2 mg QD versus placebo in adult participants with moderate-to-severe AD and a history of a prior systemic therapy failure.	Proportion of participants achieving EASI-75 at Week 16.	Estimand E1: described above. More details of Estimand E1 are described in Section 2.2.2.
		Percent change from baseline in EASI score at Week 16.	Estimand E2: The mean difference in percent change from baseline in EASI score between etrasimod 2 mg QD and placebo in patients with moderate-to-severe AD and a history of a prior systemic therapy failure. More details are described in Section 2.2.2.
Exploratory	 		

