3.5. Safety Endpoints

All the safety data will be summarized descriptively through appropriate data tabulations, descriptive statistics, and graphical presentations. Treatment-emergent AEs including SAEs and AE leading to discontinuation of study treatment, vital signs, 12-lead ECG parameters, and laboratory tests, etc. will be summarized according to the Clinical Data Interchange Standards Consortium (CDISC) and Pfizer Standards (CaPS). Treatment-emergent AE is defined as an AE that started on or after the first dose of study treatment (ie, baseline, without regard to baseline severity). The MedDRA version for AE coding at the time of database release will be adopted and the version used will be displayed in all relevant safety data tabulations. All safety analyses will be performed on the SAS (Section 4.2).

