4.2. Safety Analysis Set

The safety analysis set (SAS) will include all participants who are randomized and receive at least one dose of the study treatment (ie, etrasimod or placebo). Participants will be analyzed in the treatment groups as they receive. If a participant is treated but not randomized, then the participant will be excluded from SAS. A narrative will be provided for this participant in the CSR. The SAS will be the analysis set for safety analyses in all phases of the study.

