5.2. General Methods

In Part 1 DB, as all participants randomized to treatment groups of etrasimod 2 mg QD and placebo will switch to open-label treatment of etrasimod 2 mg QD at Week 16, the treatment labels used for reporting DB visits up to Week 16 will be "Etrasimod 2 mg QD" and "Placebo" respectively. At the end of Part 1 OLE, when reporting OLE visits from Week 20 through Week 68, the treatment labels used will be "Etrasimod 2 mg QD" and "Placebo → Etrasimod 2 mg QD" respectively to differentiate these two treatment groups.

For Part 1 DB analyses up to Week 16, the following treatment comparison will be made at each timepoint, where applicable:

• Etrasimod 2 mg QD vs. Placebo.

The primary efficacy comparison for the primary endpoint of IGA response at Week 16 will be between etrasimod 2 mg QD and placebo. For analyses after Week 16 from Week 20 through Week 68 (Part 1 OLE phase), the following treatment comparison will be made at each timepoint,

• Etrasimod 2 mg QD vs. Placebo \rightarrow Etrasimod 2 mg QD.

For Part 2 OL Safety phase, there will only be one treatment group of etrasimod 2 mg QD, the label will be "Etrasimod 2 mg QD". There is no treatment comparison in Part 2. There will be no pooling of efficacy and safety data of Part 1 and Part 2 in this study.

Descriptive Summaries

In general, the data for all continuous endpoints will be summarized by treatment group and by timepoint in tables containing descriptive statistics (N as the number of participants evaluable for the endpoint at the timepoint, mean, standard deviation, standard error of the mean, minimum, 1^{st} , 2^{nd} (ie, median) and 3^{rd} quartiles and maximum) for actual and change from baseline (or percent change from baseline) values for those endpoints measured at baseline. In case when N=1 (ie, only one participant is available/evaluable for summary), standard deviation and standard error will be reported as "NA" (not applicable) while the remaining statistical parameters will have the same value as the mean. The data for all response-type binary endpoints will be summarized by treatment group and by timepoint in tables showing descriptive statistics: N, n (ie, number of responders), response rate, standard error (SE) of the response rate, and 95% confidence interval (CI) based on normal approximation, all expressed in %. If \hat{p} is the estimated response rate, then the 95% CI is calculated as:

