Appendix 2. Data Derivation Details

Appendix 2.1. Definition and Use of Analysis Visit Windows in Reporting

There are two sets of analysis visit windows, one set for Part 1 (both DB and OLE phases) and another set for Part 2 (OL). For reporting purposes, the analysis visit windows will be used for efficacy and safety display that show by scheduled visits. Observations from all visits including scheduled, unscheduled and early termination visits will all be eligible for allocation to an analysis visit. If two or more observations fall into the same visit window, the observation closest to the target day will be used in the analysis. If there is a tie, the later observation will be used. However, for a participant who discontinues from the study early prior to Week 68 visit window in Part 1 (similarly to Week 52 visit window in Part 2), if two or more observations fall in the same visit window prior to Week 68 in Part 1 (similarly to Week 52 in Part 2), then the latest observation (rather than the observation closest to the target day) within this visit window will be used in the analysis for that visit window.

The analysis visit windowing will be applied after intercurrent events (initation of prohibited medications or discontinuation of study treatment, whichever is earlier) have been accounted for, that is, to the pre-intercurrent-event data and to all data separately (Appendix 3).

Table 8. Analysis Visit Windows for Part 1

Visit Label	Target Day ^a	Window Definition
Baseline	Day 1	Last non-missing assessment on or before Day 1 and prior to first dose of investigational product (ie, etrasimod or placebo)
Week 4	Day 29	Day 2 to Day 42
Week 8	Day 57	Day 43 to Day 70
Week 12	Day 85	Day 71 to Day 98
Week 16 ^b	Day 113	Day 99 to [Treatment Switch Day ^c or Day 126, whichever is smaller]
Week 20	Day 141	[Treatment Switch Day ^c +1 or Day 127, whichever is smaller] to Day 154
Week 24	Day 169	Day 155 to Day 196
Week 32	Day 225	Day 197 to Day 252
Week 40	Day 281	Day 253 to Day 322
Week 52	Day 365	Day 323 to Day 420
Week 68	Day 477	≥ Day 421

a. Target day is equal to the target week \times 7 days + 1 day.

b. All data collected on Week 16 visit, first open-label dose day (treatment switch day), will be included in ≤ Week 16 except for AE data, which will be included in ≥ Week 20. Any new treatment-emergent AE occurred on the day of first open-label dose (treatment switch day) will be included in ≥ Week 20.

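### The primary long-term safety displays have no exposure adjustment and no OLE-only table, so simple AE percentages cannot be read as 52-week etrasimod risk

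*SAP*

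**What the plan says.** SAP 2.2 makes this the primary endpoint for the Part 1 OLE and Part 2: "Incidence and severity of treatment-emergent AEs, AEs leading to study treatment discontinuation, SAEs, and AESIs". It gives no estimand for it.

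SAP 6.5.1 fixes the reporting periods: "TEAEs will be displayed by these 3 phases: (1) Part 1 DB (up to Week 16), (2) Part 1 DB+OLE (up to Week 68"), and Part 2 up to Week 52. No display covers the OLE alone. SAP 6.5 describes the method: "All the safety data will be summarized descriptively through appropriate data tabulations", with the layout left to the sponsor's CaPS standard. SAP 6.5.1 adds that AESIs get descriptive summaries only and that follow-up visits are included.

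Three definitions determine what the columns contain:

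- SAP 3.5: "Treatment-emergent AE is defined as an AE that started on or after the first dose of study treatment". Study treatment is etrasimod or placebo.
- SAP 4.2: "The safety analysis set (SAS) will include all participants who are randomized and receive at least one dose of the study treatment". This set serves the safety analyses of every phase.
- SAP 5.2 keeps one column per randomised arm, Etrasimod 2 mg QD and Placebo → Etrasimod 2 mg QD: "when reporting OLE visits from Week 20 through Week 68, the treatment labels used will be" these two. SAP 6.5.1 uses the same labels for TEAEs.

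Protocol 7.1.5 requires permanent discontinuation of study treatment for "Participants who do not meet EASI-50 criteria at Week 32 in Part 1 (Week 16 of OLE) or at Week 16 of Part 2".

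**The concern.** The objective is long-term safety on etrasimod, and Part 2 (about 340 participants) exists to supply that safety database. Two features stand between the planned displays and that objective.

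First, follow-up is unequal by rule. An EASI-50 non-responder in Part 2 contributes 16 treatment weeks and a responder up to 52. A percentage of all treated participants gives both the same weight, so events that would have occurred after a forced stop go unobserved while the denominator does not shrink.

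Second, one Part 1 column does not isolate etrasimod exposure. For participants randomised to placebo, the TEAE clock starts at the first placebo dose, and those who never enter the OLE remain in the column.

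Protocol 8.4.8 asks whether AESIs occur more often than expected from epidemiological or other external data. A percentage over a mixture of exposure lengths is a poor basis for that comparison when the reference is a rate per person-time.

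**Working it through.** Neither document gives a safety rate, an EASI-50 response rate or an expected exposure, so there is no figure of the plan's to reproduce. The treatment and follow-up lengths below are from the documents. The share stopped, the share not entering the OLE and the hazards are assumptions.

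**Part 2.** Let h be the hazard per 52 weeks, taken as constant (0.1 to 0.5), and f the share stopped at Week 16 (30% to 50%). Counting the 4-week follow-up for everyone, stopped participants are observed for 16 + 4 = 20 weeks and completers for 52 + 4 = 56 weeks.

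- True 52-week risk: 1 − exp(−h)
- Observed percentage: (1 − f)[1 − exp(−h × 56/52)] + f[1 − exp(−h × 20/52)]

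| f | h | Observed | 52-week risk | Ratio |
|---|---|---|---|---|
| 30% | 0.1 | 0.7 × 0.1021 + 0.3 × 0.0377 = 0.0828 | 0.0952 | 87% |
| 30% | 0.5 | 0.7 × 0.4164 + 0.3 × 0.1750 = 0.3439 | 0.3935 | 87% |
| 50% | 0.1 | 0.5 × 0.1021 + 0.5 × 0.0377 = 0.0699 | 0.0952 | 73% |
| 50% | 0.5 | 0.5 × 0.4164 + 0.5 × 0.1750 = 0.2957 | 0.3935 | 75% |

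The share stopped drives the ratio; the hazard hardly matters. Over a wider range of f, a true 10% risk (h = −ln 0.9 = 0.105) reads 9.4%, 8.0% and 6.7% with 20%, 40% and 60% stopped. Mean planned treatment falls from 52 weeks to 44.8, 37.6 and 30.4 weeks (for example 0.6 × 52 + 0.4 × 16 = 37.6). Under constant hazard, events over person-time return about 10.6 per 100 patient-years for that 10% risk, whatever the share stopped.

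**Part 1 DB+OLE, Placebo → Etrasimod column.** Placebo is 16 of 68 weeks (24%) if nobody stops. If 10% do not enter the OLE and 20-60% of entrants stop at Week 32, it is 28-37% of treatment time: 16/(16 + 0.9 × 44.8) = 28% and 16/(16 + 0.9 × 30.4) = 37%.

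To see the direction of error, take a true 52-week etrasimod risk of 10% and count treatment time only:

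- Placebo risk equal to etrasimod, no stops: 1 − exp(−0.105 × 68/52) = 12.9%.
- No placebo risk, 10% not entering the OLE, 60% of entrants stopped: 0.9 × (0.4 × 10% + 0.6 × 3.2%) = 5.3%, where 3.2% = 1 − exp(−0.105 × 16/52).

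The column can therefore read above or below the true 10%.

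**Part 1 DB+OLE, Etrasimod column.** It holds no placebo time but covers up to 68 weeks. On the same basis a true 10% reads 12.9% with no stops and 8.3% with 60% of entrants stopped and 10% not entering. It is not a 52-week figure either.

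**The case against.** **The documents do not commit to crude percentages.** This is correct. SAP 6.5.1 sends TEAEs to standard displays and leaves the layout to CaPS, which is not reproduced. A reader might infer that n (%) of all treated is the only planned form; that is inference from silence. What stands is that neither document specifies a rate, a person-time denominator or a cumulative incidence for a primary endpoint.

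**The mixing is narrow and labelled.** Also correct. It affects one of two Part 1 columns, about 30 of roughly 400 participants. The Etrasimod column and all of Part 2 contain no placebo time. The placebo period has its own DB table, and SAP Appendix 2.1 splits AEs at the switch: "Any new treatment-emergent AE occurred on the day of first open-label dose (treatment switch day) will be included in" Week 20 or later. Treatment duration is summarised in SAP 6.4.3. But in Part 1 that duration runs from the first dose of either treatment, and no planned TEAE table uses the split to show the OLE alone.

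**A reader might infer that the mixed column inflates risk.** With 0.5 events per person-year on etrasimod and 0.3 on placebo, and no stops, it reads 1 − exp(−0.5 − 0.3 × 16/52) = 44.7%, against 1 − exp(−0.5) = 39.3%. That ignores the forced stops. With all participants entering the OLE, 30-50% stopped at Week 32, those stopped counted for 20 OLE weeks and completers for 52, the column reads 34.7-38.7%, below 39.3%. With follow-up for completers as well, it reads 35.8-40.2%. No fixed direction can be claimed.

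**The SAP claims no 52-week risk.** True: it defines no safety estimand and does not pool the two parts. Incidence under a regimen that stops non-responders is a legitimate descriptive quantity. The stronger reading, that the planned results misstate 52-week risk, therefore goes too far. The supported statement is that simple percentages cannot be read as that risk.

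**A constant rate does not suit every event.** Protocol 2.3.1 describes the heart-rate effect as greatest on the first dosing day. For first-dose bradycardia or conduction delay, a later stop loses few events, a percentage is nearly unbiased, and a rate per person-year would dilute the risk. This stands and limits the remedy.

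**Conclusion.** The point holds as a gap in the specified analysis, not as proof of a wrong result. AE incidence is primary for the OLE and Part 2, yet no planned TEAE display isolates the OLE and no method accounts for follow-up that the protocol itself makes unequal. If Part 2 is summarised as a simple percentage, it would be about 73-87% of the 52-week risk, given 30-50% stopped at Week 16, a constant hazard that continues through follow-up, no other dropout, and 4 weeks' follow-up for all. In Part 1 the size and sign of the error in the Placebo → Etrasimod column depend on the placebo hazard, OLE entry and stops, none of which the documents give. First-dose cardiac events fall outside the constant-hazard argument.

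**What to change.** In SAP 6.5.1, keep the three planned displays and add:

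- (a) An etrasimod-exposed OLE table of TEAEs for the Placebo → Etrasimod group, starting at the first open-label dose and limited to participants who took it.
- (b) Exposure-adjusted incidence rates (participants with an event per 100 patient-years, with 95% CI) for TEAEs, SAEs, AEs leading to discontinuation and AESIs, counted from first etrasimod dose to last dose + 28 days. This matches the minimum 4-week post-dose AE collection in Protocol 8.4.1.

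State that n (%) remains the main summary for first-dose cardiac events.

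The inputs exist: dosing dates, AE dates and the switch-day rule in SAP Appendix 2.1. Conduct and data collection do not change. The cost is a few extra tables, and a rate that is interpretable only where the hazard is roughly constant, which a table footnote should say.
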